2.1 Primary

Dose Escalation Safety Lead-In:

- Assess the safety of tavo-EP and pembrolizumab in combination with epacadostat (CTCAE version 4)

Dose Expansion:

- Determine whether the combination of tavo-EP, pembrolizumab, and epacadostat increases the best overall response rate (BORR) in SCCHN compared with historical data for pembrolizumab monotherapy

2.2 Secondary

Dose Expansion:

- Determine the durability of clinical benefits in patients treated with tavo-EP, pembrolizumab, and epacadostat as assessed by time to progression, median PFS, median OS

2.3 Exploratory Objectives

- Determine whether the combination of tavo-EP, pembrolizumab, and epacadostat increases the objective response rate in SCCHN compared with emerging data for pembrolizumab in combination with epacadostat
- Determine the effects of combination therapy on treated and untreated lesions by examining paired biopsy specimens for changes in inflammatory gene expression, relative proportion of effector versus regulatory T cells, evaluation of inflammatory cytokines, T-cell activation, clonality, and other hallmarks of immune activation.
- Explore systemic markers of immune activation by examining circulating T-cell populations for changes in the frequency and effector function of short-lived effector cells and memory T cells.
- Explore changes in functional immune responses using Elispot and other assays.
- To explore biomarkers that inform scientific understanding of this therapeutic treatment through analysis of specimens retained for Future Biomedical Research.

2.4 Endpoints

Primary Endpoint

Dose Escalation Safety Lead-In:

- Adverse events by CTCAE version 4.0. Safety assessments include AEs (either reported by the patient or observed by the Investigator), concomitant medication use, performance status, vital signs, physical examination, and laboratory assessments. AEs will be graded and reported using CTCAE version 4 and reported descriptively.

Dose Expansion:

- Best overall response rate (BORR) by RECIST version 1.1 compared to single agent pembrolizumab. BORR is defined as the percentage of patients who attain a confirmed CR or PR over the trial with the combination treatment with a 4-week confirmatory scan per RECIST v1.1.

2.4.2 Secondary Endpoints

- Median overall survival and progression free survival. Progression free survival (PFS) is defined as the number of days from the date of enrollment to the date of progression or death regardless of cause. Patients who do not have a documented progression or death will be censored on the date of last assessment. Overall survival (OS) is defined as the number of days from the date of enrollment to the date of death regardless of cause, patients without a death date will be censored on the date last known alive.

2.4.3 Exploratory and Translational Endpoints

Best overall response rate compared to emerging data for pembrolizumab in combination with epacadostat once historical comparison data for the doublet become available.

Translational analyses are intended to be hypothesis generating. Translational endpoints will be met if there have been significant changes in:

- Inflammatory genes expression by Nanostring before and after initiation of treatment on study
- The relative proportion of effector versus regulatory T-cells in pre-treatment and post-treatment tumor specimens
- Pre-treatment versus post-treatment in cytokine expression, T-cell repertoire, clonality
- Pre-treatment versus post-treatment populations of immune cell populations in the peripheral blood including short-lived effector cells (SLECs) and memory T-cells
- Pre-treatment versus post-treatment functional immune responses using Elispot analysis

The experimental methods and statistical analysis plans for these endpoints are described in Appendix 4Translational Medicine Methods and Statistical Analysis **Appendix 4**.

3 Study Design

3.1 Characteristics

This is a multi-center, open label, 2-stage, double-arm, clinical trial in which patients in Stage 1 will receive either tavo-EP with pembrolizumab, and epacadostat (Arm A) or tavo-EP and pembrolizumab (Arm B). Based on the results of the clinical data in Stage 1, Stage 2 enroll up to an additional 26 patients.

3.2 Number of Subjects

This trial is planned for up to 68 evaluable patients.

3.3 Eligibility Criteria

Patients must have baseline evaluations performed prior to the first dose of epacadostat, pembrolizumab, or tavo-EP and must meet all inclusion and exclusion criteria. In addition, the patient must be thoroughly informed about all aspects of the study, including the study visit schedule and required evaluations and all regulatory requirements for informed consent. The written informed consent must be obtained from the patient prior to enrollment. The following criteria apply to all patients enrolled onto the study unless otherwise specified.

3.3.1 Inclusion Criteria

Patient Characteristics

1. Age \geq 18 years old;
2. ECOG performance status 0-2;
3. Life expectancy of at least 4 months;

Disease Characteristics

4. Patients must have histological or cytological diagnosis of carcinoma of the head and neck that is not amenable to surgical resection or locoregional radiation therapy with curative intent;
5. At least one accessible lesion (AL) for intratumoral injection. An AL is defined as meeting the following criteria; (1) at least 0.3 cm x 0.3 cm in longest perpendicular diameters (2) in a suitable location for application of electroporation. Tumors invading the carotid artery or at other sites that the investigator believes to be at high risk of life-threatening hemorrhage should not be injected and these lesions may not be used to meet the inclusion criterion for injectable lesions
6. Measureable disease as defined by RECIST v1.1; at least one lesion where the longest perpendicular diameter is at least 1.0 cm by clinical measurement; or at least 1.0 cm by radiographic imaging for non-nodal lesions; at least 1.5 cm in short axis by radiographic imaging for malignant lymph nodes; If the biopsied lesions were previously irradiated, they must demonstrate either radiographic or pathological evidence of recurrent or residual disease. It is not necessary that this lesion is also an AL.
7. If patient has known brain metastases, they must have stable neurologic status following local therapy (surgery or radiation) for at least 4 weeks without the use of steroids or on stable or decreasing dose of ≤ 10 mg daily prednisone (or equivalent), and must be without neurologic dysfunction that would confound the evaluation of neurologic and other AEs (patients with a history of carcinomatous meningitis are not eligible);

Treatment History

8. Patients may have had prior chemotherapy or immunotherapy or radiation therapy. Any drug related adverse events identified during prior therapy must be well controlled (typically resolution to \leq grade 1, OR resolved upon investigator review prior to initiation of this therapy);
9. No systemic antineoplastic therapy may be received by the patient between the time of the biopsy and the first administration of study treatment;

Consent for Biopsies

10. Patient must agree to any protocol mandated biopsies of tumor (deemed accessible and safe for biopsy by the investigator's assessment) and they must allow acquired tissue to be used for biomarker analysis.

Fertility

11. For women of childbearing potential, negative serum or urine pregnancy test within 14 days to the first epacadostat, pembrolizumab, or tavo-EP administration, and use of birth control from 30 days prior to the first epacadostat, pembrolizumab, or tavo-EP administration and 120 days following last day of epacadostat, pembrolizumab, or tavo-EP administration;
12. Male patients must be surgically sterile, or must agree to use contraception during the study and at least 120 days following the last day of epacadostat, pembrolizumab, or tavo-EP administration.

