- f. Alkaline phosphatase $> 2.5 \times$ ULN. Note: Subjects with 1) bone metastases and GGT $< 2.5 \times$ ULN may enroll if the alkaline phosphatase is $< 5 \times$ ULN.
- g. Total bilirubin above $1.5 \times$ the institutional ULN AND conjugated bilirubin $\geq 2.0 \times$ ULN.
- h. International normalized ratio (INR) or prothrombin time (PT) $> 1.5 \times$ ULN.
- i. Activated partial thromboplastin time (aPTT) $> 1.5 \times$ ULN.

Table 3-1: Study Calendar

Period/Procedure	Screening	Cycle 1 (42 days)				Cycle 2+ (42 days)				Safety Follow-Up	
Study Day/Visit Day	-28 to 0	1	5	8	22	1	5	8	22	30 days from Last Dose	
Informed Consent											
Informed consent	X										
Clinical Procedures											
Medical history ¹	X										
Medication review	X	X				X	X			X	X
Physical exam	X	X				X	X			X	X
Vital signs ²	X	X	X	X	X	X	X	X	X		
Performance status ³	X	X				X	X			X	X
AE assessment ⁴		X				X	X			X	X
Treatment: Dose Escalation											
Safety Lead-In and Stage 1 and Stage 2, Arm A											
tavo-EP		X	X	X		X	X	X			
Pembrolizumab		X			X	X			X		
epacadostat	Continuous oral or per G-tube dosing										
Treatment: Stage 1 and Stage, Arm B											
tavo-EP		X	X	X		X	X	X			
Pembrolizumab		X			X	X			X		
Biospecimen Collections											
Screening Labs ⁵	X										
Safety Labs ⁶		X			X	X			X		X
ECG ⁷	X					(X)					
Archival Specimen Collection	X										
Fresh biopsy ⁸	X					X					X
Research Blood (mandatory) ⁹		X				X					X
Research Blood (optional) ⁹						X			X		
Tumor Assessments											
Tumor measurements ¹⁰	X					(X)					

- ¹ Medical history includes any conditions resolved within 6 months of enrollment as well as surgeries and therapies related to the treatment of melanoma and any residual toxicity.
- ² Includes blood pressure (systolic and diastolic), respiratory rate, heart rate and temperature. Height only required at screening. Weight only required at screening and day 1 of each cycle.
- ³ ECoG
- ⁴ CTCAE version 4
- ⁵ Screening labs include CBC with platelets and differential, LFTs (AST, ALT, total bilirubin, alkaline phosphatase), PT, PTT, electrolytes, BUN, creatinine, glucose, ionized calcium, lipase, amylase, HBsAg, HCV RNA quantitative
- ⁶ Safety labs include CBC with platelets and differential, LFTs (AST, ALT, total bilirubin, alkaline phosphatase), electrolytes, BUN, creatinine, glucose, ionized calcium, lipase, amylase
- ⁷ ECGs will be performed at screening and on day 1 of each odd numbered cycle excluding cycle 1.

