4.4 Duration of Treatment

During the treatment phase, patients will receive combination therapy for 12 months or until the development of unacceptable treatment associated toxicity or confirmed progression. After the initial 12 months of therapy, patients who remain on treatment will enter the follow-up phase for the next 24 months. Patients with disease progression during the follow-up phase will have access to 12 additional months of triplet therapy. Patients who are eligible for treatment on study but who have experienced regression of all previously accessible lesions may continue on pembrolizumab and epacadostat without tavo-EP.

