4.4.1 Treatment After Disease Progression

Patients with disease progression by RECIST version 1.1 who are benefiting from treatment in the opinion of the principal investigator may continue on treatment for up to 12 months from the initiation (or re-initiation) of treatment on study.

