9.1 Birth Control, Pregnancy and Paternity

Pembrolizumab and/or tavo-EP EP may have adverse effects on a fetus in utero. Furthermore, it is not known if pembrolizumab and/or tavo-EP EP has transient adverse effects on the composition of sperm. Non-pregnant, non-breast-feeding women may be enrolled if they are willing to use 2 methods of birth control or are considered highly unlikely to conceive. Highly unlikely to conceive is defined as 1) surgically sterilized, or 2) postmenopausal (a woman who is ≥ 45 years of age and has not had menses for greater than 1 year will be considered postmenopausal), or 3) not heterosexually active for the duration of the study. The two birth control methods can be either two barrier methods or a barrier method plus a hormonal method to prevent pregnancy. Subjects should start using birth control from study Visit 1 throughout the study period up to 120 days after the last dose of study therapy.

The following are considered adequate barrier methods of contraception: diaphragm, condom (by the partner), copper intrauterine device, sponge, or spermicide. Appropriate hormonal contraceptives will include any registered and marketed contraceptive agent that contains an estrogen and/or a progestational agent (including oral, subcutaneous, intrauterine, or intramuscular agents).

Subjects should be informed that taking the study medication may involve unknown risks to the fetus (unborn baby) if pregnancy were to occur during the study. In order to participate in the study they must adhere to the contraception requirement (described above) for the duration of the study and during the follow-up period defined above. Reporting of Pregnancy and Lactation to the DSMC is required. If there is any question that a subject will not reliably comply with the requirements for contraception, that subject should not be entered into the study.

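### No pregnancy test is required after the first dose, either during the 12-month course or before the re-treatment that Section 4.4 allows

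*Combined protocol and SAP*

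**What the plan says.** **The one test.** Criterion 11 (Section 3.3.1, repeated in the synopsis) requires a "negative serum or urine pregnancy test within 14 days to the first epacadostat, pembrolizumab, or tavo-EP administration". It also sets a contraception period that ends "120 days following last day of epacadostat, pembrolizumab, or tavo-EP administration".

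**The calendar.** Table 3-1 has no pregnancy-test row. The screening panel in footnote 5 covers blood count, liver tests, then "PT, PTT, electrolytes, BUN, creatinine, glucose, ionized calcium, lipase, amylase, HBsAg, HCV RNA quantitative". Footnote 6 gives the on-treatment panel: "Safety labs include CBC with platelets and differential, LFTs (AST, ALT, total bilirubin, alkaline phosphatase), electrolytes, BUN, creatinine, glucose, ionized calcium, lipase, amylase". Neither list includes a pregnancy test.

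**Treatment and re-treatment.** Section 4.4 gives 12 months of therapy, after which "patients who remain on treatment will enter the follow-up phase for the next 24 months". It then adds: "Patients with disease progression during the follow-up phase will have access to 12 additional months of triplet therapy". Section 4.4.1 lets patients judged to be benefiting despite progression continue "for up to 12 months from the initiation (or re-initiation) of treatment on study", so restarting is clearly foreseen. The synopsis (Duration of Therapy) describes re-treatment under Arm A only; Section 4.4 names no arm.

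**Pregnancy rules.** Section 9.1 warns of possible fetal harm from pembrolizumab and/or tavo-EP and requires two birth control methods unless the woman is highly unlikely to conceive. Section 9.2 removes a subject who becomes pregnant on treatment, with monthly contact until the outcome. Section 11.7 requires pregnancy exposures to be reported to the drug suppliers within 24 hours. None of these sections schedules a test.

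**The concern.** The baseline test is tied to the first administration, so it informs the decision to dose on Cycle 1 Day 1 and nothing later. The protocol's own rules on removal and rapid reporting depend on a pregnancy being noticed, yet no procedure after enrolment looks for one.

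Re-treatment is the sharper gap. A patient may have been off drug for many months, and the contraception duty, on a literal reading, may have lapsed. She can then restart a regimen that includes agents the protocol says may harm a fetus, with no new test. What is at stake is avoidable fetal exposure.

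**Working it through.** No power or error-rate calculation applies. The check has two parts: a search for any further test, and arithmetic on the stated periods.

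**1. Search.** These places were read for a second pregnancy test:
- Synopsis and Section 3.3.1, criterion 11: one test, before the first administration.
- Table 3-1, rows and footnotes: none.
- Sections 4.4, 4.4.1 and 4.5 (treatment, continuation, follow-up): none. Section 4.4 mentions patients eligible for treatment on study, but in a sentence about omitting tavo-EP when accessible lesions have regressed. It does not re-apply the entry criteria, and criterion 11 would still refer to the first dose.
- Section 5.1 (safety assessments): none.
- Sections 9.1, 9.2 and 11.7 (contraception, pregnancy, reporting): none.

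**2. First course.** Inputs: 42-day cycles (Table 3-1) and 12 months of treatment (Section 4.4), taken as 365 days.
- Cycle starts fall on days 1, 43, ..., 337. Number = floor(364/42) + 1 = 8 + 1 = 9.
- Cycle starts after Cycle 1 Day 1 = 9 − 1 = 8, none with a required test.
- Oldest possible test at the ninth cycle start = (337 − 1) + 14 = 350 days.

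**3. Re-treatment, boundary case.** Inputs: 12 months of treatment, 24 months of follow-up (Section 4.4), contraception to 120 days after the last dose (criterion 11).
- Latest start = 12 + 24 = 36 months after the first dose. This reproduces the 36-month follow-up limit in Section 4.5.
- With the last dose of a full course near month 12, 120 days (about 4 months) ends near month 12 + 4 = 16.
- Interval from there to the latest re-treatment start = 36 − 16 = about 20 months.

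**4. Number of women.** The documents give no share of childbearing potential. If it is assumed to lie between 2% and 10%, the planned 68 patients (Section 3.2) include 0.02 × 68 = 1.4 to 0.10 × 68 = 6.8, or about 1 to 7 women exposed to the on-treatment gap. No comparable figure can be given for re-treatment. The documents do not say how many patients will reach follow-up and progress there, and the pool depends on the reading: Section 4.4 taken generally includes Arm B, while the synopsis limits re-treatment to Arm A, where lead-in patients may also be enrolled.

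**5. Tests added by the fix.**
- First course: 8 (Day 1 of Cycles 2 to 9). The screening test is already required, so its calendar entry adds none.
- Re-treatment for 12 months on the same schedule: 1 before the first dose + 8 = 9.

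**The case against.** The strongest reply is that the protocol does manage pregnancy, by another route. Section 9.1 requires two contraceptive methods and bars anyone whose compliance is in question. Section 9.2 covers a pregnancy that occurs. Section 9.3 excludes breast-feeding women. Clinical evaluation every 3 weeks on treatment, and imaging of the abdomen and pelvis at odd-numbered cycles after the first, may reveal a pregnancy. Relying on contraception plus one baseline test is a design choice, and nothing in the documents prescribes a retest interval.

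Much of this stands: the risk is reduced, and the retest interval is a matter of judgement. But none of these measures is a pregnancy test, off-treatment evaluations are only every 12 weeks, and by requiring a test before the first dose the protocol itself does not treat contraception as enough. That reasoning applies equally to a restart.

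The reply also rightly limits what can be inferred:
- A reader might take 36 months as the usual age of the test at re-treatment. It is the outer edge: the woman must complete 12 months without confirmed progression, remain in follow-up for the full 24 months, and progress at its end.
- A reader might see a contradiction in the contraception rules, since Section 9.1 also speaks of contraception "for the duration of the study and during the follow-up period defined above". That is not a separate defect. Criterion 11 governs, and for a re-treated woman the last day of administration falls in the second course, so the duty can be read as continuous. The 20-month figure holds only on the literal reading.
- A reader might conclude that the baseline test is not required because Table 3-1 omits it. Criterion 11 requires it.
- The absence of a test is established for the visible text only. Section 4.6.3.3 defers pembrolizumab administration to the package insert, which is not available here.

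**Conclusion.** The point holds as a small, inexpensive safety improvement. One test is required, before the first administration. None is required at the 8 later cycle starts of a full first course, or before re-treatment. In the boundary case re-treatment starts 36 months after the first dose, about 20 months after a literally read contraception period ends.

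These figures assume a full 12-month first course with no delays, and the 20 months assume the last dose near month 12. Few women are likely to be involved. The range of about 1 to 7 of 68 rests entirely on the assumed 2% to 10% share, and the documents support neither a count nor an upper bound for re-treated women. Nothing here affects BORR, PFS, OS or any inference from them.

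**What to change.** **(a) Section 4.4.** For women of childbearing potential, require a negative serum or urine pregnancy test within 14 days before the first re-treatment dose, with contraception in place from the decision to re-treat. No fixed waiting period is needed. If only one change is made, it should be this one.

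**(b) Table 3-1.** Add a serum or urine pregnancy test for these women at screening (the test criterion 11 already requires) and on Day 1 of each cycle from Cycle 2, taken with the existing safety laboratory samples and read before dosing. Apply the same row during re-treatment.

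**Cost.** Up to 8 added tests per woman in a full first course and about 9 in a full re-treatment course, all at existing visits except the one before re-treatment, plus an amendment to protocol and consent wording. Re-treatment waits only for the test result. The 6-week interval is a practical choice that follows the existing Day 1 samples.

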3.3.2 Exclusion Criteria

Medical History

Autoimmune

1. Active autoimmune disease that has required systemic treatment in past 2 years. Replacement therapy (e.g., thyroxine, insulin, or physiologic corticosteroid replacement therapy for adrenal or pituitary insufficiency) is not considered a form of systemic treatment;

Cardiac

2. Congestive heart failure (New York Heart Association Class III to IV);
3. History or presence of an abnormal electrocardiogram (ECG) that, in the investigator's opinion, is clinically meaningful. Screening QTc interval > 480 milliseconds is excluded. In the event that a single QTc is > 480 milliseconds, the subject may enroll if the average QTc for the 3 ECGs is < 480 milliseconds. For subjects with an intraventricular conduction delay (QRS interval > 120 milliseconds), the JTc interval may be used in place of the QTc with sponsor approval. The JTc must be < 340 milliseconds if JTc is used in place of the QTc. Subjects with left bundle branch block are excluded.
4. Uncontrolled or clinically significant conduction abnormalities (e.g., ventricular tachycardia on anti-arrhythmic are excluded), 1st degree AV block or asymptomatic LAFB/RBBB are eligible;
5. Uncontrolled, symptomatic ischemia within 6 months of first dose of study treatment or known myocardial infarction in the previous six months;
6. Patients with electronic pacemakers or defibrillators;

Pulmonary

7. Evidence of interstitial lung disease or active, noninfectious pneumonitis including symptomatic and/or pneumonitis requiring treatment;

Oncologic

8. Any other current or previous malignancy within the past 2 years that, in the opinion of the Principal Investigator will interfere with study-specific endpoints;

Infectious

9. Evidence of significant active infection (e.g., pneumonia, cellulitis, wound abscess, etc.) requiring systemic therapy at time of study enrolment;
10. Hepatitis B – Most NPC patients have been infected with hepatitis B (Cancer Epidemiol Biomarkers Prev. 2015. 24:1766-73, N = 711) and, therefore, the inclusion of healthy patients with a history of hepatitis B is a central part of this study. In addition, PD-1 antibodies have been proven to be safe in patients with active hepatitis and hepatocellular carcinoma (e. g. KEYNOTE 224). However, patients with HBV surface antigen positive (HBsAg) must have AST and total bilirubin < 1.5 x ULN AND:
 11. Negative HBV RNA PCR OR;
 12. On antivirals for HBV AND at least 8 weeks of prior anti-PD1 antibody therapy AND no history of AST or total bilirubin levels > 1.5 x ULN due to PD-1 antibody therapy
 13. Hepatitis C (HCV RNA [qualitative] is detected).

Gastrointestinal

14. Presence of a gastrointestinal condition that may affect drug absorption. Administration of epacadostat through a feeding tube is permitted.

Medications / Medication Reactions

15. Patients receiving systemic steroid therapy for a chronic inflammatory condition. Topical steroids, nasal and inhaled steroids are permitted. Prednisone or equivalent ≤ 10 mg/day is permitted as hormone replacement; higher dosage prednisone should be stopped at least 14 days prior to C1D1;

16. Receipt of live attenuated vaccine within 30 days before the first dose of study treatment. Examples of live vaccines include, but are not limited to, the following: measles, mumps, rubella, chicken pox, yellow fever, rabies, *Bacillus Calmette-Guérin* (BCG), and typhoid vaccine. Seasonal influenza vaccines for injection are generally killed virus vaccines and are allowed; however, intranasal influenza vaccines (eg, FluMist[®]) are live attenuated vaccines and are not allowed.

17. Subjects receiving Monoamine Oxidase Inhibitors (MAOIs) or drug which has significant MAOI activity (meperidine, linezolid, methylene blue) within the 21 days before screening.

18. Any history of Serotonin Syndrome (SS) after receiving serotonergic drugs.

19. Use of any UGT1A9 inhibitor from screening through follow-up period, including the following: diclofenac, imipramine, ketoconazole, mefenamic acid, and probenecid.

20. Known allergy or reaction to any component of epacadostat, pembrolizumab, or tavo-EP formulation.

Laboratories

21. Screening Laboratory Abnormalities

- a. Absolute neutrophil count (ANC) $< 1.0 \times 10^9/L$.
- b. Platelets $< 75 \times 10^9/L$.
- c. Hemoglobin $< 9 \text{ g/dL}$ or $< 5.6 \text{ mmol/L}$ (transfusion is acceptable to meet this criterion).
- d. Serum creatinine $\geq 1.5 \times$ institutional upper limit of normal (ULN) OR measured or calculated creatinine clearance (glomerular filtration rate can also be used in place of creatinine or CrCl) $< 50 \text{ mL/min}$ for subjects with creatinine levels $> 1.5 \times$ institutional ULN.
- e. AST or ALT $> 2.5 \times$ institutional ULN.
- f. Alkaline phosphatase $> 2.5 \times$ ULN. Note: Subjects with 1) bone metastases and GGT $< 2.5 \times$ ULN may enroll if the alkaline phosphatase is $< 5 \times$ ULN.
- g. Total bilirubin above $1.5 \times$ the institutional ULN AND conjugated bilirubin $\geq 2.0 \times$ ULN.
- h. International normalized ratio (INR) or prothrombin time (PT) $> 1.5 \times$ ULN.
- i. Activated partial thromboplastin time (aPTT) $> 1.5 \times$ ULN.

Table 3-1: Study Calendar

Period/Procedure	Screening	Cycle 1 (42 days)				Cycle 2+ (42 days)				Safety Follow-Up	
Study Day/Visit Day	-28 to 0	1	5	8	22	1	5	8	22	30 days from Last Dose	
Informed Consent											
Informed consent	X										
Clinical Procedures											
Medical history ¹	X										
Medication review	X	X				X	X			X	X
Physical exam	X	X				X	X			X	X
Vital signs ²	X	X	X	X	X	X	X	X	X		
Performance status ³	X	X				X	X			X	X
AE assessment ⁴		X				X	X			X	X
Treatment: Dose Escalation											
Safety Lead-In and Stage 1 and Stage 2, Arm A											
tavo-EP		X	X	X		X	X	X			
Pembrolizumab		X			X	X			X		
epacadostat	Continuous oral or per G-tube dosing										
Treatment: Stage 1 and Stage, Arm B											
tavo-EP		X	X	X		X	X	X			
Pembrolizumab		X			X	X			X		
Biospecimen Collections											
Screening Labs ⁵	X										
Safety Labs ⁶		X			X	X			X		X
ECG ⁷	X					(X)					
Archival Specimen Collection	X										
Fresh biopsy ⁸	X					X					X
Research Blood (mandatory) ⁹		X				X					X
Research Blood (optional) ⁹						X			X		
Tumor Assessments											
Tumor measurements ¹⁰	X					(X)					

- ¹ Medical history includes any conditions resolved within 6 months of enrollment as well as surgeries and therapies related to the treatment of melanoma and any residual toxicity.
- ² Includes blood pressure (systolic and diastolic), respiratory rate, heart rate and temperature. Height only required at screening. Weight only required at screening and day 1 of each cycle.
- ³ ECoG
- ⁴ CTCAE version 4
- ⁵ Screening labs include CBC with platelets and differential, LFTs (AST, ALT, total bilirubin, alkaline phosphatase), PT, PTT, electrolytes, BUN, creatinine, glucose, ionized calcium, lipase, amylase, HBsAg, HCV RNA quantitative
- ⁶ Safety labs include CBC with platelets and differential, LFTs (AST, ALT, total bilirubin, alkaline phosphatase), electrolytes, BUN, creatinine, glucose, ionized calcium, lipase, amylase
- ⁷ ECGs will be performed at screening and on day 1 of each odd numbered cycle excluding cycle 1.
- ⁸ Fresh biopsy collection will be done at screening, Cycle 2 Day 1, and at progression/end of treatment. Additional biopsies may be performed if clinically indicated.
- ⁹ Research blood requirements are described in *Section 10*. Mandatory blood collection will occur on Cycle 2, Day 1; Optional sample collection will occur on Day 22 for Cycles 2 and beyond and then on Day 1 for Cycles 3 and beyond. Additional research blood acquisition, storage, and distribution information is provided in *Section 10*. Every effort shall be made to collect mandatory post-treatment (follow-up) research blood samples, but failure to collect this sample due to patient refusal or logistical constraints shall not constitute a protocol deviation or violation.
- ¹⁰ MRI, contrast-enhanced CT, or PET/CT imaging of the face, neck, chest, abdomen, and pelvis are required at screening and on day 1 of each odd-numbered cycle excluding cycle 1. Both clinical and radiographic measurements may be used. All superficial, clinically apparent lesions that cannot be adequately assessed radiographically (e. g. subcutaneous lesions) must be numbered and photographed with a metric ruler visible in each photograph. For photographed lesions with borders that are not clearly visible, investigators should trace the lesions' outline, making a solid line with a felt-tipped pen. Visible lesions should never be circled with a solid line but dashed or dotted lines may be used to distinguish these markings from the borders of otherwise invisible lesions. Tumor assessments will be made using RECIST version 1.1. IL-12 plasmid dosing may be based on the most recent tumor measurements and measurements need not be repeated immediately prior to each tavo-EP treatment.
- ¹¹ Epacadostat dose may be changed if indicated based on dose escalation safety run-in described below in Table 4-1.

